13.5 Detail of Laboratory Assessments and Procedures

13.5.1 Local Laboratory at Investigational Site

The laboratory tests specified in this section will be performed in the laboratory at the investigational site. All local laboratories must use the isotope dilution mass spectroscopy method for the serum creatinine assay. All efforts should be made to take the blood sample from a clean new venous site, or the second option could be a central venous line to collect the blood specimen. Site personnel should not draw the blood sample from an existing peripheral venous access site or a line used for IV fluid administration. See Site/Investigator's Study Manual for additional details regarding blood drawing technique.

13.5.1.1 Serum Electrolytes & Biochemistry

The following assessments are required at baseline, then once daily during treatment (max 15 days), daily until Day 14 or hospital discharge (whichever occurs first), and at the 30-day follow-up visit, regardless of treatment status:

- Creatinine level.
- Blood urea nitrogen (BUN) (not collected at 30-day follow-up).

If SCr and/or BUN assessments are performed more than once daily as part of the subject's medical care, all values are to be recorded on the eCRF.

Terlipressin
Protocol MNK19013058
Incorporating Amendments 1, 2 and 3

The following assessments are required at baseline, then once daily during treatment with study drug (max 15 days):

- Sodium.
- Potassium.
- Chloride.
- HCO_{3.}

The following assessments are required at baseline, on Treatment Days 1, 3, 7, and whenever possible, at treatment termination:

- Total bilirubin.
- Alkaline phosphatase (ALP).
- Alanine aminotransferase (ALT).
- Aspartate aminotransferase (AST).
- Total protein.
- Albumin.
- Magnesium.
- Calcium.
- Glucose.

13.5.1.2 Hematology

The following assessments are required at baseline, on Treatment Days 1, 3, 7, and whenever possible, at treatment termination:

- International normalized ratio (INR).
- Complete blood count (CBC) and differential.

13.5.2 Total Volume of Blood Collected

The total volume of blood collected from each subject over the course of 14 days and end of study will be approximately 310 mL.

If subjects agree to participate in the biomarker study an additional blood sample of approximately 10 mL will be collected.

13.6 Detail of Efficacy Assessments and Procedures

Serum creatinine must be collected at baseline, once daily during treatment (see Section 13.5.1.1); and then once daily (regardless of treatment status) until Day 14 or hospital discharge, whichever occurs first. If SCr assessments are performed more than once daily as part of the subject's medical care, all values obtained each day will be recorded on the eCRF. Serum creatinine values obtained after RRT, TIPS, liver transplant, or open-label vasopressor use will be excluded from the efficacy evaluation. The qualifying serum creatinine for subjects on prior vasopressors will be taken after completion of vasopressor washout.

13.6.1 Primary Efficacy Variable

Incidence of verified HRS reversal, defined as the percentage of subjects with 2 consecutive SCr values no more than 1.5 mg/dL at least 2 hours apart, while on treatment by Day 14 or discharge (on treatment defined as up to 24 hours after the final dose of study drug). Subjects must be alive without RRT for at least 10 days after achieving verified HRS reversal. SCr values after RRT, TIPS, liver transplant, or open-label vasopressor use will be excluded from primary endpoint analysis. SCr values obtained after midodrine administration will be included if midodrine was started on Day 1, was administered for no more than 24 hours, and the subject was enrolled on or after 17 August 2018. SCr values will also be included if obtained after the administration of a single dose of dobutamine.

[figure not shown]
SCr data for the primary end point will be collected at least daily until discharge or Day 14. The analysis will be based on ITT population. Treatment should be continued until 24 hours after a second confirmatory SCr value no more than 1.5 mg/dL has been obtained, OR up to a maximum of 14 days (maximum of 15 days if SCr first reaches 1.5 mg/dL on Day 14). The date and time of the first observed SCr value of no more than 1.5 mg/dL (HRS reversal) will be used for calculating the time window for the verifying SCr value. The next (consecutive) SCr value of no more than 1.5 mg/dL must occur during the time window in order to have a verified HRS reversal. The date RRT is instituted for the first time will be used to determine if a subject underwent RRT by Day 30.

[figure not shown]

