5.4.1 Primary Endpoint Rationale

HRS reversal, defined as at least 1 SCr measurement of no more than 1.5 mg/dL, has been used for decades to determine treatment response in published HRS clinical studies and is the standard endpoint utilized in the literature and in HRS treatment guidelines (Arroyo et al, 1996; Salerno et al, 2007; Angeli et al, 2015). The reversal of HRS Type 1 represents a dramatic clinical response to treatment: for the endpoint to be achieved, the rapid progression of renal failure must be arrested and normal renal function restored. The purpose of the primary end point of "verified" HRS reversal is to verify that the first SCr value of no more than 1.5 mg/dL is not a spurious laboratory value. An additional element of the primary endpoint requirement, ie, alive without RRT, has been added to demonstrate the short term durability of the primary end point on clinical outcomes. RRT is defined as any procedure to replace non-endocrine kidney function and includes intermittent hemodialysis, ultrafiltration, continuous hemofiltration and hemodialysis, peritoneal dialysis and other dialysis and filtration techniques.

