6.1 Efficacy Variables

The efficacy variables are summarized below and further details are provided in Section 13.6.

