6.1.1 Primary Efficacy Variables

The primary efficacy evaluation will be based on the following:

Incidence of verified HRS reversal, defined as the percentage of subjects with 2 consecutive SCr values no more than 1.5 mg/dL at least 2 hours apart, while on treatment by Day 14 or discharge (on treatment defined as up to 24 hours after the final dose of study drug). Subjects must be alive without RRT for at least 10 days after achieving verified HRS reversal. SCr values after RRT, transjugular intrahepatic portosystemic shunt (TIPS), liver transplant, or open-label vasopressor use will be excluded from primary end point analysis. SCr values obtained after midodrine administration will be included if midodrine was started on Day 1,

was administered for no more than 24 hours, and the subject was enrolled on or after 17 August 2018. SCr values will also be included if obtained after the administration of a single dose of dobutamine.

Note: SCr data for primary end point will be collected at least daily until discharge or Day 14. The analysis will be based on the Intent to Treat (ITT) population.

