13.1 Schedule of Assessments and Procedures

Table 13–1 presents the schedule of assessments and procedures to be performed during the study.

Table 13–1 Schedule of Assessments

Study Assessment		Pre- Treatment Period			Follow-up Period (Days from 1st Dose) ^c											
	Screening	Baseline Assessment	Days 1	to 14 ^a	as a	pplic	able)				End of Treatment	10 Days After 2 nd SCR ≤ 1.5 mg/dL	Day 14 b or Discharge whichever occurs first			
	Period		1	2	3	4	5	6	7	8 to 14 ^a				30 days $\pm 10 d^{t}$	60 days ± 14 d	90 days ± 14 d
Diagnosis of HRS Type 1	X															
Informed consent	X															
Inclusion/exclusion criteria	X	X														
Verification of study qualification	X															
Demographics	X															
Height and body weight	X															
Pregnancy test d	X															
Prior medications	X	X														
Record all pre- enrollment paracentesis prior to randomization e,f	X	X														
Baseline SCr prior to randomization f	X	X ^g														
Randomization		X														
Medical history h	X	X				_								X		

Study Assessment		Pre- Treatment Period			Follow-up Period (Days from 1st Dose)											
	Screening	Baseline Assessment	Days 1 t	to 14 ^a	(as a	pplica	able)				End of Treatment	10 Days After 2 nd SCR ≤ 1.5 mg/dL	Day 14 b			
	Period		1	2	3	4	5	6	7	8 to 14 ^a			or Discharge whichever occurs first	30 days ± 10 d ^t	60 days ± 14 d	90 days ± 14 d
Physical examination (including weight and height)		x ⁱ	x ^u	x ^u	xu	xu	x^{u}	x^{u}	xu	x ^u				x^{i}		
12-lead ECG ^j		X														
Child-Pugh score		X														
Urine sample for biomarkers		Х														
Blood sample for biomarkers		Х														
Venous blood lactate		X														
Study drug administration as applicable			X	X	X	X	X	X	X	X						
Daily Assessments (1	regardless of	treatment status	s)													
Record albumin dose administered		X	X	X	X	X	X	X	X	X	X		X			
SCr & BUN ^m		X	X	X	X	X	X	X	X	X	X		X	χ^{m}		

Study Assessment	Screening Period	Pre- Treatment Period				Follow-up Period (Days from 1st Dose)										
		Baseline Assessment	Days 1 t	to 14 ^a	(as a	pplica	able)				End of Treatment	10 Days	Day 14 b			
			1	2	3	4	5	6	7	8 to 14 ^a		After 2 nd SCR ≤ 1.5 mg/dL	or Discharge whichever occurs first	30 days ± 10 d ^t	60 days ± 14 d	90 days ± 14 d
Confirmatory SCr at minimum of 2 hours after initial SCr of ≤ 1.5 mg/dL			Х	х	x	x	x	X	X	Х	Х		x ⁿ			
Site to confirm subject survival for verified reversal												Х				

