^JA 12-lead ECG will be performed at baseline. Clinically relevant abnormalities found will be reported on the medical history page. The investigator may perform additional unscheduled examinations to manage or evaluate a suspected AE as clinically necessary.

^kBoth urine and blood samples for biomarker evaluation will be collected once at baseline; participation in this project will not affect participation in the main study.

Treatment should be continued until 24 hours after 2 consecutive SCr values no more than 1.5 mg/dL have been obtained, OR up to a maximum of 14 days (maximum of 15 days if SCr first reaches 1.5 mg/dL on Day 14, when the Day 14 assessments will be performed on Day 15). Window is (± 30 minutes).

mMust be performed at least once daily during active treatment AND until Day 14 (regardless of treatment status) or discharge, whichever occurs first. If SCr and/or BUN assessments are performed more than once daily as part of the subject's medical care, all values are to be recorded on the eCRF. At 30-day follow-up visit, collect SCr only (no BUN).

ⁿA blood sample for measurement of SCr must be drawn before discharge. The second verifying sample of SCr no more than 1.5 mg/dL must be taken at least 2 hours apart and must be consecutive.

^oIf a subject meets the primary end point (2 consecutive SCr values of no more than 1.5 mg/dL), the subject's survival and RRT status must be confirmed 10 days after the date of the second SCr. This follow up is required regardless of whether the subject remains hospitalized or has been discharged. If the subject has been discharged, follow-up may be by phone.

PRequired for evaluation of efficacy endpoints.

 $^{^{}q}$ Vital sign measurements include body temperature, respiratory rate, systolic and diastolic blood pressure, SpO₂ (pulse oximetric saturation), and heart rate. Time points for systolic and diastolic blood pressure and heart rate: predose and postdose at 5 (\pm 2) min and 2 (\pm 0.25) h for every dose. Time points for body temperature, respiratory rate, and pulse oximetric saturation (SpO₂): once daily.

^rConcomitant medications include IV solutions and blood products.

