15.3.6.1 Primary Efficacy Analysis

Incidence of verified HRS reversal is defined as the percentage of subjects with 2 consecutive SCr values no more than 1.5 mg/dL at least 2 hours apart, while on treatment by Day 14 or discharge (on treatment defined as up to 24 hours after the final dose of study drug). The subject must be alive without RRT for at least 10 days after achieving verified HRS reversal. SCr values after RRT, TIPS, liver transplant, or open-label vasopressor use will be excluded from primary end point analysis. SCr values obtained after midodrine administration will be included if midodrine was started on Day 1, was administered for no more than 24 hours, and the subject was enrolled on or after 17 August 2018. SCr values will also be included if obtained after the administration of a single dose of dobutamine.

Verified HRS reversal will be summarized by treatment group and analyzed using a Z Score based on the upper alpha boundary values for the interim and final analyses. The upper alpha boundary value for the interim analysis is 2.79651. At the interim analysis, if the Z score

is greater than 2.79651 then the study will stop for early success. If the Z score is no more than 2.79651 then the study will continue to the final analysis. The final analysis will be successful if the Z score is greater than 1.97743.

Table 15–2 shows the number of subjects with HRS Type 1 reversal that will be needed to achieve success at the interim analysis if the estimate of the placebo rate is accurate (approximately 12.5%).

Table 15–2: Potential Scenarios for Success at the Interim Analysis with a Placebo Rate of Approximately 12.5%

Endpoint	Terlipressin (N = 100) n (%)	Placebo (N = 50) n (%)	Z Score
Scenario 1	34 (34.0)	6 (12.0)	2.8723
Scenario 2	36 (36.0)	7 (14.0)	2.8098

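### Does the primary endpoint need a new rule for which pair of creatinine values verifies HRS reversal?

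*Combined protocol and SAP*

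**What the plan says.** The short definition appears in the synopsis, in Section 6.1.1 ("2 consecutive SCr values no more than 1.5 mg/dL at least 2 hours apart, while on treatment by Day 14 or discharge"), in the opening sentence of Section 13.6.1 and in Section 15.3.6.1 ("Incidence of verified HRS reversal is defined as the percentage of subjects with 2 consecutive SCr values no more than 1.5 mg/dL"). None of these says that the pair must begin with the first low value. The fourth secondary endpoint (Sections 13.6.2 and 15.3.6.2) repeats the same wording.

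Section 13.6.1 then goes further. "The date and time of the first observed SCr value of no more than 1.5 mg/dL (HRS reversal) will be used for calculating" the verification window, and "The next (consecutive) SCr value of no more than 1.5 mg/dL must occur during the time window in order to have a verified HRS reversal".

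Other places bear on the reading:

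- Section 6.1 introduces its definitions as a summary and adds that "further details are provided in Section 13.6".
- Section 5.4.1 gives the aim of verification: to "verify that the first SCr value of no more than 1.5 mg/dL is not a spurious laboratory value".
- Table 13-1 has a row for "Confirmatory SCr at minimum of 2 hours after initial SCr", and Section 13.2.3.2 also times the repeat from the first value.
- Footnote n of Table 13-1 says: "The second verifying sample of SCr no more than 1.5 mg/dL must be taken at least 2 hours apart and must be consecutive".

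SCr is drawn at least daily, and Section 13.6 has every extra routine-care value recorded.

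**The concern.** Two kinds of subject seem to have no settled status.

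(a) The first low value is followed by a higher one, the subject stays on treatment, and a valid pair appears later. The short definition counts this subject. The window in Section 13.6.1, read literally, does not.

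(b) A routine draw falls less than 2 hours after the first low value. No sentence says outright whether that draw is passed over or breaks the pair.

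This is the primary endpoint, and the interim success scenarios in Table 15-2 lie close to the boundary. If the rule were chosen after treatment codes were known, the choice could be challenged.

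**Working it through.** **Classification.** Each pattern below was read under the short definition (any consecutive pair at least 2 hours apart) and under the first-value rule of Section 13.6.1. The 10-day survival and RRT condition is taken as met. In both columns a recorded short draw counts as a value.

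| SCr (mg/dL) at hours | Any pair | First value |
|---|---|---|
| 1.4 at 0, 1.3 at 24 | yes | yes |
| 1.4 at 0, 1.6 at 24, 1.4 at 48 | no | no |
| 1.5 at 0, 1.7 at 24, 1.4 at 48, 1.3 at 72 | yes | no |
| 1.4 at 0, 1.4 at 1, 1.3 at 24 | yes | no |
| 1.4 at 0, 1.6 at 1, 1.3 at 24 | no | no |

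The last two rows would change only if the 1-hour draw were ignored: the fourth row would become a responder under the first-value rule, and the fifth under both. Footnote n requires the verifying sample to be both consecutive and at least 2 hours later, so no current text supports ignoring a recorded value. In the fifth row 1.4 and 1.3 are not consecutive. In the fourth row the 1-hour and 24-hour values already form a valid pair 23 hours apart, so the only question is whether a later pair counts. Part (b) therefore reduces to part (a).

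**Effect on Z.** Table 15-2 is reproduced by the pooled two-proportion statistic, Z = (p1 − p2) / √[p̄(1 − p̄)(1/n1 + 1/n2)]. Scenario 1 has p1 = 0.34, p2 = 0.12, p̄ = 40/150 = 0.2667, so Z = 0.22 / √(0.2667 × 0.7333 × 0.03) = 0.22 / 0.07659 = 2.8723, as printed. Scenario 2 gives 2.8088 against a printed 2.8098. Both exceed the boundary of 2.79651, so the slip does not matter here.

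| Interim, 100 v 50 | Z |
|---|---|
| 34 v 6 (Scenario 1) | 2.872 |
| 33 v 6 (one terlipressin responder lost) | 2.764 |
| 34 v 5 (one placebo responder lost) | 3.159 |
| 32 v 5 (2% of subjects lost in each arm) | 2.947 |
| 28 v 5 (about one responder in six lost in each arm) | 2.509 |
| 36 v 7 (Scenario 2) | 2.809 |
| 35 v 7 (one terlipressin responder lost) | 2.700 |

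For 28 v 5, p̄ = 33/150 = 0.22 and Z = 0.18 / √(0.22 × 0.78 × 0.03) = 0.18 / 0.07175 = 2.509.

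At the final analysis (200 v 100, boundary 1.97743), with 12/100 on placebo as an assumption close to the 12.5% of Table 15-2:

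| Final, 200 v 100 | Z |
|---|---|
| 43 v 12 | 2.005 |
| 42 v 12 | 1.913 |
| 41 v 11 (1% of subjects lost in each arm) | 2.049 |

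Moving from the short definition to the first-value rule can only remove responders, but it can do so in either arm. Z falls or rises according to where they are lost.

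**The case for a change.** The strongest opposing case is that deferring to Section 13.6.1 does not fully settle the matter. That section holds both formulations, and a later pair satisfies its opening sentence. The phrase about the next value can mean the next draw or the next low draw, and the readable text gives the window no upper limit. Unverified first values do occur: Section 5.3.2 reports that in REVERSE the rates were 24% v 15% for a single low value and 20% v 13% once confirmation was required. In both scenarios of Table 15-2, losing one terlipressin responder turns success into failure.

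Part of this stands. Section 15.3.6.1 repeats the short definition without pointing to Section 13.6.1, and no readable sentence says that a later pair fails.

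The rest carries less weight. Failure of a later pair follows from an unmet necessary condition, and Section 5.4.1, Table 13-1 and Section 13.2.3.2 all look to the first value. REVERSE used a 48-hour confirmation rule, and Section 5.3.2 names discharge before the confirmatory sample as one reason for missing significance. A subject lost that way has no later pair, so both readings agree. One responder deciding the result at a boundary is true of any binary endpoint, and these examples were placed at the boundary and remove responders from one arm only.

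**Conclusion.** This is a gap that analysts can fill sensibly. The statistical section gives the summary definition and Section 13.6.1 the detail, which leans to the strict answer: verification belongs to the first low value. A programmer who follows either reading exactly, blind and identically in both arms, obtains a valid endpoint and a valid test. No stated figure depends on the choice.

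The size cannot be estimated from the documents. The subjects concerned need an unverified first low value followed by a valid pair while still on treatment, and they are probably few. Each reclassified terlipressin responder is worth about 0.11 in Z at the interim and 0.09 at the final analysis near the boundaries shown, and the net direction is unknown.

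An amendment would reopen primary-endpoint text that Amendment 1 revised after the Special Protocol Assessment letter, without improving the design.

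The conclusion assumes that the rule is programmed before treatment codes are known. It also allows that the figures in Section 13.6.1 and the text of Section 15.3.6.3, which are not in the public copy, may already state it.

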13.6.2 Secondary Efficacy Variables

- Incidence of subjects with HRS reversal, defined as the percentage of subjects with a SCr value no more than 1.5 mg/dL while on treatment by Day 14 or discharge (SCr values after RRT, TIPS, liver transplant, or open-label vasopressor use will be excluded).
- Durability of HRS reversal: the percentage of subjects with HRS reversal without RRT to Day 30. HRS reversal is defined as the percentage of subjects with a SCr value no more than 1.5 mg/dL while on treatment by Day 14 or discharge (SCr values after RRT, TIPS, liver transplant, or open-label vasopressor use will be excluded). RRT is defined as any procedure to replace non-endocrine kidney function and includes intermittent hemodialysis, ultrafiltration, continuous hemofiltration and hemodialysis, peritoneal dialysis and other dialysis and filtration techniques. The date RRT is instituted for the first time will be used to determine if a subject underwent RRT by Day 30.
- Incidence of HRS reversal in the SIRS subgroup: the percentage of SIRS subjects with HRS reversal. HRS reversal is defined as the percentage of subjects with a SCr value no more than 1.5 mg/dL while on treatment by Day 14 or discharge (SCr values after RRT, TIPS, liver transplant, or open-label vasopressor use will be excluded). The SIRS subgroup is defined as any subject with at least 2 of the following criteria: WBC less than 4,000 or greater than 12,000 cells/μL; heart rate greater than 90 bpm; temperature greater than 38°C or less than 36°C; respiratory rate greater than 20/min; HCO₃ less than 21 mmol/L; the latter criterion represents an approximation of the SIRS criterion PaCO₂ of less than 32 mm Hg, derived from the observed HCO₃ in subjects with HRS in whom a PaCO₂ value was available (from the TAHRS study) and the calculated HCO₃ in subjects with decompensated liver disease and PaCO₂ of less than 32 mm Hg.

Incidence of verified HRS reversal without HRS recurrence by Day 30 is defined in Section 10.5. Incidence of verified HRS reversal, defined as the percentage of subjects with 2 consecutive SCr values no more than 1.5 mg/dL at least 2 hours apart, while on treatment up to 24 hours after the final dose of study drug, by Day 14 or discharge. Subjects must be alive without RRT for at least 10 days after achieving verified HRS reversal. SCr values after RRT, transjugular intrahepatic portosystemic shunt (TIPS), liver transplant, or open-label vasopressor use will be excluded from primary end point analysis. SCr values obtained after midodrine administration will be included if midodrine was started on Day 1, was administered for no more than 24 hours, and the subject was enrolled on or after 17 August

2018. SCr values will also be included if obtained after the administration of a single dose of dobutamine.

14 Adverse Events

The investigator will carefully collect a thorough first dose of study drug baseline information and history for each subject upon enrollment. Immediately after a subject receives the first dose of study drug, throughout the duration of the study treatment and at each evaluation, the investigator will determine whether any AE has occurred. The investigator will also instruct the subject to contact the investigator or designee in between study visits and throughout the entire study period to report any AEs, until otherwise instructed.

Terlipressin
Protocol MNK19013058
Incorporating Amendments 1, 2 and 3

The investigator will record the nature, causality, severity, treatment and outcome of the AE, and will determine whether there is a "reasonable probability" that the study drug treatment caused the event.

A data safety monitoring board (DSMB) will review safety data throughout the study, as outlined in the DSMB charter.

